**Table 9: Dose Level Modification Guideline for the Phase I, Part A Dose Escalation**

	Starting Dose	One Dose Reduction	Two Dose Reductions
Dose Level 1	30 mg daily	15 mg daily	15 mg every other day
Dose Level 2	60 mg daily	30 mg daily	15 mg daily
Dose Level 3	120 mg daily	60 mg daily	30 mg daily
Dose Level 4	210 mg daily	120 mg daily	60 mg daily
Dose Level 5	300 mg daily	210 mg daily	120 mg daily
Dose Level 6	360 mg daily	300 mg daily	210 mg daily

**Table 10: Dose Modification Guideline for Phase I, Part B Dose Expansion and Phase 2**

Starting Dose (mg daily)	First Dose Reduction (mg daily)	Second Dose Reduction (mg daily)	Third Dose Reduction (mg daily)
120	90	75	45
90	75	60	30
75	60	45	30
60	45	30	15
45	30	15	not applicable
30	15	not applicable	not applicable
15	not applicable	not applicable	not applicable

### 8.11 Treatment Duration

In the absence of unacceptable OP-1250 treatment-related toxicity or disease progression, subjects may receive OP-1250 treatment for up to 1 year and beyond 1 year with the agreement of the investigator or designee and the sponsor.

Treatment will continue until any 1 of the following occurs:

- SAE or AE that requires dose discontinuation as described in [Section 8.10, Table 8](#).
- Progressive disease as determined by RECIST 1.1 (see [Appendix E](#)) (Tumor marker elevations in the absence of unequivocal radiologic progression of target or non-target lesions is not considered disease progression. Per RECIST 1.1, disease progression requires an overall disease burden increase based on the change in non-measurable disease that is comparable in magnitude to the increase that would be required to declare PD for measurable disease: ie, an increase in tumor burden representing an additional 73% increase in 'volume,' which is equivalent to a 20% increase in diameter in a measurable lesion.)
- Initiation of non-protocol anticancer therapy.
- Illness or condition that may interfere with the subject's participation or require treatment discontinuation.
- Treating investigator or designee's determination that continuation of protocol therapy is not in the subject's best interests.
- Pregnancy.
- Noncompliance.
- Voluntary withdrawal of consent.
- Sponsor termination of the study.

### 8.12 Blinding

This is an open-label study with no placebo or comparators.

	OP-1250-001	Page 71 of 111
---	-------------	----------------

### 8.13 Prior and Concomitant Medications

All prescription and over-the-counter medications, including vaccinations, taken by a subject within 30 days before the first study drug administration will be recorded in the designated electronic CRF (eCRF).

The following actions should be considered with the following medications/therapies:

- PPIs should be avoided and are prohibited during the first 2 cycles of therapy. After that, PPI may be used only if other methods of symptom control have been ineffective. The Medical Monitor should be notified if PPI are started. The use of H2 blockers is strongly discouraged. If the subject experiences symptoms of gastric acid reflux that are not relieved with conservative measures (small meals, no eating after 6 PM, avoiding foods that stimulate stomach acid such as caffeine, alcohol, tomatoes, spicy foods), the investigator or designee may prescribe H2 blockers to be taken once or twice a day provided they are taken at least 2 hours prior to (or post) the OP-1250 dose; however, 4 hours is preferred.
- No other cancer therapies or investigational agents are permitted during the entire duration of the study treatment.

Based on the in vitro drug-drug interaction profile of OP-1250, the types of concomitant medications to avoid or to use with caution are presented in [Table 11](#).

**Table 11: Types of Concomitant Medications to Avoid or Use with Caution**

Concomitant Medication Types	OP-1250 Characteristic	Potential Effects of Co-Administration	Approach
Prolongs QT	Unknown	Possible increased risk of Torsades de Pointes	Avoid (see Appendix C )
Strong CYP3A4 Inhibitors or Inducers	Metabolized primarily by CYP3A4	OP-1250 levels may be increased if administered with CYP3A4 inhibitors or decreased with CYP3A4 inducers	Avoid (see Appendix B )
P-gp substrates and BCRP substrates	Potential inhibitor of intestinal P-gp	May increase drug levels of concomitant medications that are substrates for intestinal P-gp (eg, digoxin) and BCRP substrates (eg, sulfasalazine)	Use P-gp and BCRP substrates with narrow therapeutic index with caution (see Appendix D )
Substrates of CYP2C8 and CYP2C9	Potential time dependent inhibitor of CYP2C8 and CYP2C9	May increase drug levels of concomitant medications that are substrates for CYP2C8 (eg, repaglinide) or CYP2C9 (eg, [S]-warfarin)	Use CYP2C8 and CYP2C9 substrates with narrow therapeutic index with caution (see Appendix D )
PPIs and H2 Blockers	Absorption may be affected by gastric pH.	Co-administration may affect the absorption of OP-1250	PPIs should be avoided and are prohibited during the first 2 cycles of therapy. The use of H2 blockers is strongly discouraged. (See the first bullet point of Section 8.13 for full details.)

Abbreviations: CYP = cytochrome P450 isozyme; H2 = histamine 2 receptor; P-gp = P-glycoprotein; PPI = proton pump inhibitor

Although in vitro, OP-1250 appears to be a substrate, primarily, of CYP3A4 and as such its exposure may be increased by CYP3A4 inhibitors (eg, itraconazole) and reduced by CYP3A4 inducers (eg, rifampin), results from in vivo studies are not yet available. Therefore, subjects should avoid strong CYP3A4 inhibitors or inducers if possible. However, their use in this study is not exclusionary.

Pre- and perimenopausal women must take an LHRH agonist of physician's choice.

Medications for nausea, vomiting, diarrhea, and constipation may be given according to the standard of care guidelines at the discretion of the investigator or designee. Granisetron (or other) is preferred over ondansetron due to the potential prolongation of the QT interval with ondansetron.

Bisphosphonates or other bone modifying agents are allowed provided the subject has been on these agents for at least 4 weeks prior to Cycle 1.

Subjects who have febrile neutropenia (FN) should receive antibiotics per standard of care. G-CSF may be used at the investigator or designee's discretion.

Other medications considered necessary for the subject's safety and well-being may be given at the discretion of the investigator. Any concomitant medications added or discontinued during the study should be recorded in the eCRF.

#### **8.14 Treatment Compliance**

The importance of treatment compliance should be emphasized to the subject. Subjects will be given take-home kits and detailed instructions on how to take medications at home. Subjects will be instructed to return all used and unused study drug containers at each study visit. Subject compliance with the dosing regimen will be assessed by reconciliation of the used and unused study drug at each clinic visit. The quantity dispensed, returned, used, lost, etc., must be recorded on the dispensing log provided for the study. Compliance will be monitored and documented by site personnel on the appropriate form. The site personnel will question the subject regarding adherence to the dosing regimen by reviewing dosing dates and times on the used bottles, recording the number of capsules and strengths returned, the date returned, and determining treatment compliance before dispensing new medication to the study subject.

#### **8.15 Investigational Product Accountability**

The investigator or designee is responsible for maintaining accurate records (including dates and quantities) of IP received, subjects to whom IP is dispensed (subject-by-subject dose specific accounting), and IP lost or accidentally or deliberately destroyed. Any unused capsules shall be returned and be reviewed by the site staff and sponsor's monitor before they are destroyed. The investigator or designee must retain all unused or expired study supplies until the Olema Pharmaceuticals designated monitor has confirmed the accountability data.

##### **8.15.1 Return and Disposition of Clinical Supplies**

Unused study drug must be kept in a secure location for accountability and reconciliation by Olema Pharmaceuticals designated monitor. The investigator or designee must provide an explanation for any destroyed or missing study drug or study materials.

Unused study drug may be destroyed on site, per the site's standard operating procedures, but only after Olema Pharmaceuticals or its designee has granted approval for drug destruction. The Olema Pharmaceuticals designated monitor must account for all study drug in a formal reconciliation process prior to study drug destruction. All study drug destroyed on site must be documented. Documentation must be provided to Olema Pharmaceuticals or its designee and retained in the investigator's study files. If a site is unable to destroy study drug appropriately, the site can return unused study drug to Olema Pharmaceuticals' designee upon request. The return of study drug or study drug materials must be accounted for on a Study Drug Return Form provided by Olema Pharmaceutical's designee.

All study drug and related materials should be stored, inventoried, reconciled, and destroyed or returned according to applicable state and federal regulations and study procedures.

#### **8.16 Dietary or Other Protocol Restrictions**

Subjects should be advised to avoid grapefruit/grapefruit juice, Seville orange/Seville orange juice, and St. John's wort due to the possibility of interactions of these substances with the pharmacokinetics of OP-1250.

## 8.17 Efficacy, Safety, and Additional Variables

The Schedule of Events in [Table 1](#), [Table 2](#), [Table 3](#), and [Table 4](#) describe the timing of required evaluations.

### 8.17.1 Efficacy Variables

Efficacy variables include overall response (CR and PR) as determined by the subject's best tumor response, clinical benefit rate, [REDACTED] Overall response (CR and PR) as determined by the subject's best tumor response, clinical benefit rate, [REDACTED] will be assessed using RECIST 1.1 (see [Appendix E](#)), which includes evaluation of both the CNS and non-CNS compartments. [REDACTED]

### 8.17.2 Safety Variables

Safety will be assessed by periodic physical examinations, 12-lead ECGs, clinical laboratory assessments, and monitoring of AEs. Additional clinical laboratory assessments and 12-lead ECGs will also be obtained when clinically indicated.

### 8.17.3 Additional Variables

- [REDACTED]:
- I [REDACTED]
  - I [REDACTED]
  - I [REDACTED]
  - I [REDACTED]
  - I [REDACTED]

## 9 DEFINITION OF AN ADVERSE EVENT

An AE is any unfavorable and unintended sign, symptom, or disease temporally associated with the use of an investigational (medicinal) product or other protocol-imposed intervention, regardless of attribution. An AE may include inter-current illnesses or injuries that represent an exacerbation (increase in frequency, severity, or specificity) of pre-existing conditions (eg, worsening of asthma). Whenever possible, it is preferable to record a diagnosis as the AE term rather than a series of symptoms relating to a diagnosis. In NCI-CTCAE, v 5.0, unequivocal neoplastic disease progression is captured as the verbatim term of disease progression under the System Organ Class “General”. When an AE of disease progression meets the requirements to be considered serious, the verbatim term should be reported as disease progression and should not be reported as an SAE. Evidence that the AE or death was a manifestation of underlying disease (eg, radiological changes suggesting tumor growth or progression: clinical deterioration associated with a disease process) should be documented in the EDC.

The reporting period for AEs is the period from administration of the first dose of study drug through 30 days after the last administration of study drug. All related AEs will be followed to resolution, stabilization, or loss of contact with the subject. All unrelated AEs will be followed until the time of the Safety Follow-up visit, which is between 30 to 42 days after the EOT visit.

The investigator will assess AEs for severity, for relationship to IP, and whether the event meets 1 or more of the definitions of an SAE (see [Section 9.1](#)).

The investigator will determine the severity of each AE and will record it on the source documents and in the AE eCRF, using NCI-CTCAE, v 5.0.

The investigator will determine the relationship of an AE to the IP and will record it on the source documents and in the AE eCRF. All AEs should be considered related to the study drug unless such relationship can be definitely excluded.

In order to classify AEs and diseases, preferred terms will be assigned by the sponsor or its designee to the original terms entered in the eCRF, using MedDRA.

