
 
To estimate the ORR of OP-1250 in subjects with HR-positive/HER2-negative metastatic or locally advanced breast cancer with no evidence of CNS metastases who have progressed following at least 1 hormonal therapy regimen in the metastatic or locally advanced setting.
 
	
 
ORR by evaluation of tumor response assessments using RECIST 1.1 in subjects without evidence of CNS metastases who have measurable disease.
 

 
To assess the safety and tolerability of OP-1250.
 
	
 
Incidence, nature, and severity of TEAEs and SAEs according to NCI-CTCAE version 5.0.
 

 
To assess the plasma PK of OP-1250.
 
	
 
Plasma levels of OP-1250 at pre-defined intervals to establish PK parameters (includes <math>C_{max}</math>, <math>C_{min}</math>, <math>T_{max}</math>, AUC, <math>t_{1/2}</math>, and OP-1250 trough concentration at steady state).
 

Secondary Objectives	Secondary Endpoints

 
To estimate the CBR of OP-1250 in subjects with HR-positive/HER2-negative metastatic or locally advanced breast cancer with no evidence of CNS metastases who have progressed after receiving at least 1 hormonal treatment regimen in the metastatic or locally advanced setting.
 
	
 
CBR, as defined by percent of subjects with a CR + PR + SD for <math>\geq 24</math> weeks, by evaluation of tumor response assessments using RECIST 1.1 in subjects without evidence of CNS metastases.
 

	

[REDACTED]

Exploratory Objectives	Exploratory Endpoints

[REDACTED]

	

[REDACTED]

[REDACTED]

	

[REDACTED]

[REDACTED]

	

[REDACTED]

[REDACTED]

	

[REDACTED]

[REDACTED]

	

[REDACTED]

Abbreviations: AUC = area under the curve; C = Cycle; CBR = clinical benefit rate;  $C_{\max}$  = maximum concentration;  $C_{\min}$  = minimum concentration;

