### 9.1 Serious Adverse Events

A SAE is defined as any AE that:

- Results in death (ie, the AE actually causes or leads to death).
- Is life threatening (ie, the AE, in the view of the investigator, places the subject at immediate risk of death. It does not include an AE that, had it occurred in a more severe form, might have caused death).
- Requires or prolongs in-patient hospitalization.
- Results in persistent or significant disability or incapacity (ie, the AE results in substantial disruption of the subject’s ability to conduct normal life functions).
- Results in a congenital anomaly or birth defect in a neonate/infant born to a mother exposed to IP prior to conception or during pregnancy.

- Is considered a significant medical event by the investigator based on medical judgment (eg, may jeopardize the subject or require medical or surgical intervention to prevent 1 of the outcomes listed above).

The reporting period for SAEs is the period from administration of the first dose of study drug through 30 days after the last administration of study drug. SAEs reported to the investigator outside of this reporting period will be reported to Olema Pharmaceuticals or its designee if, in good medical judgment, the event has any bearing on the study data. SAEs must be followed by the investigator until resolution, or until the subject is lost to follow-up, even if this extends beyond the study-reporting period. Resolution of an SAE is defined as the return to baseline status or stabilization of the condition with the expectation that it will remain chronic.

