13.2 Adverse Events

Adverse events will be collected from the time of signing of the informed consent until 30 days following the last dose of study treatment or until resolution/stabilization of any ongoing drug related AEs.

All AE summaries will be restricted to TEAEs, which are defined as those AEs with onset or worsening after the first administration of study drug till the 30 days following the last dose of study drug or any study drug related AEs. [Appendix A](#) contains rules for how partial dates will be handled. If it cannot be determined whether the AE is treatment emergent due to a partial onset date, then it will be counted as such. Verbatim terms in the eCRFs will be mapped to (PT and SOC using MedDRA. Adverse events will be assigned a severity grade per NCI-CTCAE version 5.0. For summaries of maximum CTCAE grade, at each level of subject summarization, a subject is classified according to the highest grade if the subject reported 1 or more events. For summaries of TEAEs that are related to OP-1250, a TEAE is considered related to OP-1250 if it is reported by the Investigator as related, probably related, or possibly related.

AE summaries will be presented by OP-1250 dose using SAF set. Summaries that are displayed by SOC and PTs will be ordered by descending frequency of the total column by SOC and by descending frequency of PT within SOC. Summaries of the following types will be presented:

- Overall summary of TEAEs that contain an overview of each item below.
- Subject incidence of DLTs and total number of unique DLTs by MedDRA SOC and PT in the DLT evaluable analysis set.
- Subject incidence of TEAEs and total number of unique TEAEs by MedDRA SOC and PT.
- Subject incidence of grade 3 or greater TEAEs and total number of unique grade 3 or greater TEAEs by MedDRA SOC and PT.
- Subject incidence of OP-1250-related TEAEs and total number of unique OP-1250-related TEAEs by MedDRA SOC and PT.
- Subject incidence of grade 3 or greater OP-1250-related TEAEs and total number of unique grade 3 or greater OP-1250-related TEAEs by MedDRA SOC and PT.
- Subject incidence of TEAEs by MedDRA SOC, PT, and maximum CTCAE grade.
- Subject incidence of serious TEAEs and total number of unique serious TEAEs by MedDRA SOC and PT.
- Subject incidence of OP-1250-related serious TEAEs and total number of unique OP-1250-related serious TEAEs by MedDRA SOC and PT.
- Subject incidence of TEAEs leading to death as an outcome by MedDRA SOC and PT.

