- Subject incidence of TEAEs leading to OP-1250 treatment discontinuation, dose reduction and drug withheld by MedDRA SOC and PT.

If any adverse events of special interest (AESI) are identified throughout the study, subject incidence of each AESI and the total number of unique AESIs will be presented.

Separate listings of all SAEs, all AEs leading to OP-1250 treatment discontinuation, and all AEs resulting in death will be provided. A listing of all deaths will also be presented.

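### Progression recorded as an adverse event enters the TEAE tables but not the serious-TEAE table, and the SAP has no rule for it, so the primary safety tables do not reconcile

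*Protocol*

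**What the plan says.** Protocol Section 9 notes that under CTCAE v5.0 "unequivocal neoplastic disease progression is captured as the verbatim term of disease progression" in the general system organ class. For an adverse event of progression that meets a seriousness criterion, the instruction is that "the verbatim term should be reported as disease progression and should not be reported as an SAE". The same section has the investigator judge each adverse event against the serious-event definition in Section 9.1, and sets a reporting period from first dose to 30 days past the last.

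The first criterion in Section 9.1 is "Results in death (ie, the AE actually causes or leads to death". No exception for progression appears there.

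In both phases a primary endpoint in Protocol Table 5 is "Incidence, nature, and severity of TEAEs and SAEs according to NCI-CTCAE version 5.0".

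SAP 13.2 limits its summaries to TEAEs and lists the tables. They cover all TEAEs, Grade 3 or higher, serious, related, "Subject incidence of TEAEs leading to death as an outcome by MedDRA SOC and PT" and "Subject incidence of TEAEs leading to OP-1250 treatment discontinuation, dose reduction and drug withheld by MedDRA SOC and PT". None removes or separates progression terms.

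On deaths, Protocol 11.2 plans a listing without those related to progression. The synopsis (Safety Analyses) and SAP 13.2 each plan a listing of all deaths.

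**The concern.** Treatment runs until RECIST progression or another stopping reason (Protocol 8.11), so progression tends to be found while the TEAE window is still open. If a site enters it as an adverse event, lack of efficacy is counted in tables meant to describe tolerability. If the event is fatal, it appears in the fatal table and is missing from the serious table. A reader of the study report would then see more fatal TEAEs than fatal serious TEAEs, with nothing in the plan to explain the gap.

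The counts would also depend on a convention that the protocol does not write down. Two sites could handle identical cases differently and both be within Section 9. If progression, or the habit of recording it, differs between dose groups, the by-dose safety columns planned in SAP 6.1 would reflect that as well as toxicity.

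**Working it through.** **The plan's own figure.** The precision attached to safety event rates in Phase II is ±15% with 50 subjects (Protocol 11.4.3). It reproduces: the exact 95% interval at 25/50 runs from 35.5% to 64.5%, a half-width of (64.5 − 35.5)/2 = 14.5 points. It is not in dispute. It describes sampling error around whatever is counted, and does not settle whether progression is counted. The rest is a matter of rules, not arithmetic.

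**Tracing one death through the rules.** Compare a subject who dies of progression that was entered as an adverse event, with onset inside the window, with a subject who dies of another adverse event in the same window.

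| Output | Progression death entered as AE | Other fatal AE |
|---|---|---|
| All TEAEs (SAP 13.2) | counted | counted |
| Grade 3 or higher TEAEs (SAP 13.2) | counted | counted |
| TEAEs leading to death (SAP 13.2) | counted | counted |
| Serious TEAEs (SAP 13.2) | not counted | counted |
| Listing of SAEs (SAP 13.2) | absent | present |
| Listing of AEs resulting in death (SAP 13.2) | present | present |
| Listing of all deaths (SAP 13.2, synopsis) | present | present |
| Listing of deaths (Protocol 11.2) | absent | present |

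The Grade 3 or higher row follows because a fatal event takes the top CTCAE grade; Protocol 11.2 groups Grades 3, 4 and 5. The serious rows follow from Section 9 as written. Under Section 9.1 alone, both subjects would be in them.

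**The gap in one line.** Let F be subjects with a fatal TEAE, S those with a fatal serious TEAE, and P those whose only fatal TEAE is progression. Then F − S = P. Each such death opens a gap of one. If the site does not enter the progression as an adverse event, P does not rise, and that death appears only in the listing of all deaths.

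**Non-fatal progression.** If entered as an adverse event in the window, it counts under all TEAEs, and under Grade 3 or higher if so graded. It counts under discontinuation only if the record names the event as the cause of stopping. It could also reach the related-TEAE tables, since "All AEs should be considered related to the study drug unless such relationship can be definitely excluded", although an investigator may often be able to exclude a relationship to drug for progression.

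**Where progression is already removed.** It is excluded from DLTs (Protocol 8.8.2, SAP 13.1), from dose modification (Protocol 8.10) and from the Protocol 11.2 death listing. The TEAE summaries have no matching rule.

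**The case against.** The strongest reply is that Section 9 does not order every RECIST progression onto the adverse event form. It describes how CTCAE names the term, and its instruction covers the narrower case of a progression event that is serious. Protocol 8.11 lists adverse events and RECIST progression as separate reasons to stop, Protocol 8.3.3 separates progression from toxicity, and SAP 9.1 tabulates the primary reason for stopping treatment. This stands. A reader might infer that most subjects who stop for progression would show up as having a TEAE leading to discontinuation; the documents do not support that. Protocol 8.8.4 reports no discontinuations due to an adverse event among 37 Part B subjects. It does not say how many had progressed, so it neither shows nor rules out the effect.

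A second reply is that Section 9 is a specific exception to the general rule in 9.1, so there is no true contradiction. That is a fair reading of intent. Section 9.1 does not mention the exception, however, and Section 9 sends the investigator to 9.1 to judge seriousness. Even if the exception is accepted, the mismatch between the fatal and serious tables remains.

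A third is that nothing is hidden: tables by preferred term would show progression as its own row, and the SAP lists every death. That also stands. A separate row does not correct the any-TEAE or Grade 3 or higher totals, though, or explain why the fatal and serious counts differ.

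**Conclusion.** The point holds as an inconsistency between rules that feed a primary safety endpoint. Any progression entered as an adverse event in the TEAE window enters the TEAE tables, and each progression death so entered is a fatal and Grade 3 or higher TEAE but not a serious one. The three statements on listing deaths cannot all be followed.

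The number of subjects affected cannot be worked out, because the documents neither require nor report how often progression is recorded as an adverse event.

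Three stronger readings are not supported. First, fatal toxicity is not made non-serious: the mismatch covers only deaths from progression, which stay visible in the SAP listings. Second, keeping progression out of SAE reporting is not itself the fault; the fault is allowing it as an adverse event with no cross-reference in 9.1 and no analysis rule. Third, MTD determination is not affected, because the DLT definition already excludes progression. The matter is worth correcting before database lock.

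**What to change.** 1. **Protocol Sections 9 and 9.1.** State in Section 9 whether progression of the disease under study is recorded as an adverse event. Add to 9.1 a cross-reference to the Section 9 exception so that the two agree.
2. **SAP 13.2.** Exclude terms coded to progression of the disease under study from the TEAE incidence, Grade 3 or higher, discontinuation and fatal-TEAE summaries. Show them in one separate table and listing. Tabulate all deaths by cause: disease progression, adverse event, other. The exclusion is still useful if progression is declared not to be an adverse event, because it catches entries already made.
3. **Protocol 11.2.** Align the death listing with the synopsis and SAP 13.2, which list all deaths.

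The cost is a preferred-term filter, a separate progression table and listing, a table of deaths by cause, and wording changes. No new data are collected. The downside is that the list of progression terms needs a medical check before database lock.
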